**6.4 Guidelines for the Management of Elevated Phosphate Levels**

Guidelines for the clinical management of elevated serum phosphate levels are presented below.

**Guidelines for Management of Serum Phosphate Elevation**

Serum Phosphate Level	Study Drug Management	Medical Management
All subjects in the study	Continue erdafitinib treatment.	Restriction of phosphate intake to 600 – 800 mg/day.

5.6-6.9 mg/dL (1.8-2.3 mmol/L)
	
Continue erdafitinib treatment.
	
Restriction of phosphate intake to 600 – 800 mg/day. May consider sevelamer: Children 1-2 years: sevelamer 100-140 mg/kg/day divided TID titrated to desired phosphate level Children ≥ 2 years: sevelamer initial dose: 400 or 800 mg TID with food; titrate to desired phosphate level at monthly intervals in 1200 mg/day increments (ie, 400 mg at each meal) up to a maximum of 1,600 mg PO TID with food

7.0-9.0 mg/dL (2.3-2.9 mmol/L)
	
Withholda erdafitinib treatment until serum phosphate level returns to <5.5 mg/dL (or baseline).  Then re-start treatment at the same dose.  A dose reduction may be implemented for persistentb hyperphosphatemia (≥7 mg/dL) lasting > 1 week if clinically necessary
	
Restriction of phosphate intake to 600 – 800 mg/day.  Children 1-2 years: sevelamer 100-140 mg/kg/day divided TID until phosphate level is <5.5 mg/dL. Children ≥ 2 years: sevelamer initial dose: 400 or 800 mg TID with food; titrate at monthly intervals in 1200 mg/day increments (ie, 400 mg at each meal) up to a maximum of 1,600 mg PO TID with food until phosphate level is <5.5 mg/dL.

>9.0 mg/dL (>2.9 mmol/L)
	
Withholda erdafitinib treatment until serum phosphate level returns to <5.5 mg/dL (or baseline).  Re-start treatment at the reduced dose outlined in Appendix IV.
	
Restriction of phosphate intake to 600 – 800 mg/day.  Sevelamer: Children 1-2 years: 100-140 mg/kg/day divided TID Children ≥ 2 years: initial dose: 400 or 800 mg TID with food; titrate at monthly intervals in 1200 mg/day increments (ie, 400 mg at each meal) up to a maximum of 1,600 mg PO TID with food AND Acetazolamide 5-7.5 mg/kg/dose (up to 250 mg/dose) BID or TID only until serum phosphate level returns to <5.5 mg/dL.


>10.0 mg/dL (>3.2 mmol/L) and/or significant alteration in baseline renal function and/or Grade 3 hypercalcemia
	
Erdafitinib should be discontinued permanently. (In situations where the subject is having clinical benefit and the study chair agrees that re-starting drug is in the best interest of the subject, the drug may be re-introduced at the reduced dose level outlined in Appendix IV if appropriatec. Follow other recommendations described above.)
	
Medical management as clinically appropriate.

Note: These are general guidelines that are based on emerging data and consensus experience of participating investigators and/or the experts in the field. The treating physicians must use clinical judgment and local standard of care to decide the best way to manage phosphate elevation. If sevelamer hydrochloride is not available, the use of other phosphate binders (non-calcium containing) based on the local standard is recommended. These guidelines will be updated based on emerging data. Additional information on phosphorous in foods by class of food can also be found at www.permanente.net/homepage/kaiser/pdf/42025.pdf. Additional information for phosphate management and diet can be found the National Kidney Foundation website (http://www.kidney.org/atoz/content/phosphorus.cfm) a. Drug interruptions for hyperphosphatemia suggested to be 7 days duration
		

b. Persistent hyperphosphatemia is considered to be more than 1 sequential phosphate value of  $\geq 7$  mg/dL

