**3.1.2 IRB Approval**

Each investigator or group of investigators at a clinical site must obtain IRB approval for this protocol and submit IRB approval and supporting documentation to the CTSU Regulatory Office before they can be approved to enroll patients. For CTEP and Division of Cancer Prevention (DCP) studies open to the National Clinical Trials Network (NCTN) and NCI Community Oncology Research Program (NCORP) Research Bases after March 1, 2019, all U.S.-based sites must be members of the NCI Central Institutional Review Board (NCI CIRB). In addition, U.S.-based sites must accept the NCI CIRB review to activate new studies at the site after March 1, 2019. Local IRB review will continue to be accepted for studies that are not reviewed by the CIRB, or if the study was previously open at the site under the local IRB. International sites should continue to submit Research Ethics Board (REB) approval to the CTSU Regulatory Office following country-specific regulations.

Sites participating with the NCI CIRB must submit the Study Specific Worksheet for Local Context (SSW) to the CIRB using IRBManager to indicate their intent to open the study locally. The NCI CIRB's approval of the SSW is automatically communicated to the CTSU Regulatory Office, but sites are required to contact the CTSU Regulatory Office at [[contact]](mailto:[contact]) to establish site preferences for applying NCI CIRB approvals across their Signatory Network. Site preferences can be set at the network or protocol level. Questions about

establishing site preferences can be addressed to the CTSU Regulatory Office by email or calling [name].

Sites using their local IRB or REB, must submit their approval to the CTSU Regulatory Office using the Regulatory Submission Portal located in the Regulatory section of the CTSU website. Acceptable documentation of local IRB/REB approval includes:

- Local IRB documentation;
- IRB-signed CTSU IRB Certification Form; and/or
- Protocol of Human Subjects Assurance Identification/IRB Certification/Declaration of Exemption Form.

In addition, the Site-Protocol Principal Investigator (PI) (i.e. the investigator on the IRB/REB approval) must meet the following criteria in order for the processing of the IRB/REB approval record to be completed:

- Holds an active CTEP status;
- Active status at the site(s) on the IRB/REB approval (*applies to US and Canadian sites only*) on at least one participating organization's roster;

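### Section 6.4 phosphate table: 6.9 mg/dL is printed as 2.3 mmol/L instead of 2.2, so 2.3 mmol/L stands in both the continue and the withhold row and 2.26-2.29 mmol/L falls only in continue

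*Combined protocol and SAP*

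**What the plan says.** Section 6.4 gives each phosphate band in mg/dL, with mmol/L in parentheses. Two adjacent rows matter here.

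- **Continue row**, "5.6-6.9 mg/dL (1.8-2.3 mmol/L": treatment goes on, with dietary phosphate restriction. The phosphate binder is optional: "May consider sevelamer".
- **Withhold row**, "7.0-9.0 mg/dL (2.3-2.9 mmol/L": the site withholds "erdafitinib treatment until serum phosphate level returns to" below 5.5 mg/dL or baseline. "Then re-start treatment at the same dose" follows. Sevelamer is listed without the optional wording.

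A footnote adds: "Drug interruptions for hyperphosphatemia suggested to be 7 days duration". The table note makes the whole scheme guidance: "The treating physicians must use clinical judgment and local standard of care to decide the best way to manage phosphate elevation".

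Section 5.4.1.4 refers back to this table for hyperphosphatemia as a dose-limiting toxicity. It uses a threshold of 7.0 and prints no unit.

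**The concern.** The same value, 2.3 mmol/L, is printed as the top of the continue row and the bottom of the withhold row, while the mg/dL limits (6.9 and 7.0) are distinct. At the next cut the table separates rows with a strict inequality (above 9.0 mg/dL, above 2.9 mmol/L). At 2.3 there is no tie-break, and no sentence states which unit governs.

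This cut decides whether the drug is held and whether the binder is optional. A site working from the mmol/L figures could continue treatment where the mg/dL figures call for a hold. The protocol foresees sites abroad (Section 3.1.2: "International sites should continue to submit Research Ethics Board (REB) approval"), but it does not say in which units any site reports.

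**Working it through.** **Inputs.** The five distinct limits printed in both units in the Section 6.4 table are 5.6/1.8, 6.9/2.3, 7.0/2.3, 9.0/2.9 and 10.0/3.2 (mg/dL / mmol/L). The conversion factor is not in the documents. I take it from the atomic mass of phosphorus: 1 mg/dL = 10/30.974 = 0.32285 mmol/L.

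**Step 1: reproduce the printed figures** (mg/dL × 0.32285, rounded to one decimal).

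| mg/dL | mmol/L | Rounded | Printed |
|---|---|---|---|
| 5.6 | 1.808 | 1.8 | 1.8 |
| 6.9 | 2.228 | **2.2** | **2.3** |
| 7.0 | 2.260 | 2.3 | 2.3 |
| 9.0 | 2.906 | 2.9 | 2.9 |
| 10.0 | 3.229 | 3.2 | 3.2 |

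Four pairs reproduce; the 6.9 pair does not.

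**Step 2: check without the outside constant.** A pair (x, y) rounded to one decimal requires a factor between (y − 0.05)/x and (y + 0.05)/x. Among the four other pairs, the highest lower bound is 2.25/7.0 = 0.3214 and the lowest upper bound is 3.25/10.0 = 0.325. Within that range 6.9 mg/dL is 2.218 to 2.243 mmol/L, which is 2.2 throughout. Reaching 2.3 from 6.9 needs a factor of at least 2.25/6.9 = 0.3261. That would make 10.0 mg/dL 3.26, or 3.3, against the printed 3.2. So the 6.9 entry disagrees with the rest of its own table.

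**Step 3: convert back around the cut** (mmol/L ÷ 0.32285).

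| mmol/L | mg/dL | Row by mmol/L as printed | Action by 7.0 mg/dL cut |
|---|---|---|---|
| 2.24 | 6.94 | continue | continue |
| 2.25 | 6.97 | continue | continue |
| 2.26 | 7.00 | continue only | withhold |
| 2.27 | 7.03 | continue only | withhold |
| 2.28 | 7.06 | continue only | withhold |
| 2.29 | 7.09 | continue only | withhold |
| 2.30 | 7.12 | both rows | withhold |

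Five two-decimal readings conflict. The width is 2.300 − 2.260 = 0.040 mmol/L, or 7.12 − 7.00 = 0.12 mg/dL. A laboratory reporting to one decimal meets the conflict at one value, 2.3.

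The lower end is tight: 2.26 mmol/L is 7.0001 mg/dL with 10/30.974 but 6.999 with the rounded factor 0.3229. Readings of 2.27 and above are clearly over 7.0 with either.

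**The case against.** The strongest reply is that this is a one-digit slip in a secondary unit.

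- **mg/dL is implied as the governing unit.** The restart level, the binder endpoint and the definition of persistent hyperphosphatemia are in mg/dL only. The 7.0 in Section 5.4.1.4 makes sense only in mg/dL. A mmol/L site must convert anyway to apply the restart level. This is a fair reading, but it is inference; no sentence says so, and the printed mmol/L figures invite direct use.
- **Rounding contributes to the 2.26-2.29 band.** Those readings miss the withhold row because 2.260 was properly rounded up to 2.3. Changing only the wrong figure to 2.2 would leave them in neither row. Rounding also produces mismatches elsewhere: 3.21 and 3.22 mmol/L (9.94 and 9.97 mg/dL) exceed the 3.2 limit for permanent discontinuation while below 10.0 mg/dL. This stands, and it means the correction needs an explicit cut as well as a new digit. It does not undo the effect of the wrong limit, which places these readings in the continue row.
- **The consequence is small.** The excess over the cut is at most 0.12 mg/dL, the hold ends in a restart at the same dose, sevelamer is available in both rows, and phosphate is rechecked weekly in Cycle 1 and before later cycles (Section 8.1). The international-site text is general regulatory wording and shows no actual mmol/L reporting. All of this holds, and it limits the weight of the point. But clinical judgment is a poor substitute for a table that gives two opposite instructions for one printed value.

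**Conclusion.** The concern holds. The printed 2.3 mmol/L for 6.9 mg/dL is wrong and should be 2.2. As written, 2.30 mmol/L falls in two rows with opposite instructions, and 2.26-2.29 mmol/L falls only in the continue row although it is at least 7.0 mg/dL. The only outside input is the conversion factor; the error in the 6.9 entry shows without it, from the table's other four pairs.

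The practical impact is low. How often a reading lands in the band, and whether any site works in mmol/L, cannot be determined from the documents. The response endpoint, sample size and decision rule do not depend on this figure. It merits correction because it is an operative threshold in a safety table.

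**What to change.** In the next amendment, change the continue row to 5.6-6.9 mg/dL (1.8-2.2 mmol/L). Add one line for two-decimal reports: continue below 2.26 mmol/L, withhold at 2.26 mmol/L or above. Readings of 2.24 and 2.25 then continue, 2.26 and above are withheld, and nothing is left between the rows.

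Alternatively, add one line saying that the mg/dL value governs and that mmol/L results must be converted before the table is used. That line should say that the converted value is compared unrounded with 7.0, since 2.25 mmol/L (6.97 mg/dL) would otherwise round to 7.0.

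The cost is one corrected figure and one added line, or the single added line. No mg/dL threshold changes, and no new data, visits or patients are needed.

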**5.4.1 Non-Hematological Dose-Limiting Toxicity**

- 5.4.1.1 Any Grade 3 or greater non-hematological toxicity attributable to the investigational drug with the specific exclusion of:
- Grade 3 nausea and vomiting of < 3 days duration
  - Grade 3 liver enzyme elevation, including ALT/AST/GGT that returns to

levels that meet initial eligibility criteria or baseline within 7 days. See [Section 6.3](#), and [Appendix XI](#) for values that represent thresholds between CTCAE grades.

Note: For the purposes of this study the ULN for ALT is defined as 45 U/L regardless of baseline.

- Grade 3 or 4 fever < 5 days duration.
- Grade 3 infection < 5 days duration.
- Grade 3 hypophosphatemia, hypokalemia, hypocalcemia or hypomagnesemia responsive to supplementation

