5.4.1.2 Any Grade 1 visual disturbance that persists for  $\geq 4$  weeks

5.4.1.3 Any Grade 2 non-hematological toxicity that persists for  $\geq 7$  days and is considered sufficiently medically significant or sufficiently intolerable by patients that it requires treatment interruption.

Note: Allergic reactions that necessitate discontinuation of study drug will not be considered a dose-limiting toxicity.

5.4.1.4 Hyperphosphatemia will be reported as a DLT if a dose modification is required (as described in [Section 6.4](#) for serum phosphate of 7.0 or greater)

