**6.2 Dose Modifications for Non-Hematological Toxicity**

- 6.2.1 If a patient experiences non-hematological dose-limiting toxicity as defined in [Section 5.4.1](#), the treatment will be held. If the toxicity resolves to meet eligibility parameters or baseline within 14 days of drug discontinuation, the patient may resume treatment at a reduced dose as outlined in the dosing nomogram table in [Appendix IV](#). Doses reduced for toxicity will not be re-escalated, even if there is minimal or no toxicity with the reduced dose.
- 6.2.2 If a non-hematologic dose-limiting toxicity as defined in [Section 5.4.1](#) does not resolve to meet eligibility or baseline parameters within 14 days of drug discontinuation, the patient must be removed from protocol therapy. Any Grade 1 visual disturbance that persists for  $\geq 4$  weeks and does not resolve to meet eligibility or baseline parameters within  $\geq 4$  weeks of drug discontinuation must be removed from protocol therapy.
- 6.2.3 If non- hematologic dose-limiting toxicity recurs in a patient who has resumed treatment at the reduced dose, the patient must be removed from protocol therapy.

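### Sections 5.4.1.4, 6.2 and 6.4 give inconsistent stop and restart actions for the same phosphate or calcium event, and the protocol does not say which governs

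*Combined protocol and SAP*

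**What the plan says.** **What counts as a DLT.** Section 5.4.1.1 covers "Any Grade 3 or greater non-hematological toxicity attributable to the investigational drug with the specific exclusion of" a short list. The electrolyte item on that list is "Grade 3 hypophosphatemia, hypokalemia, hypocalcemia or hypomagnesemia responsive to supplementation". Hypercalcemia is not on it, so attributable Grade 3 hypercalcemia is a DLT. For phosphate, 5.4.1.4 says "Hyperphosphatemia will be reported as a DLT if a dose modification is required", and points to 6.4 for values of 7.0 mg/dL or more.

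**General rule, 6.2.** Every non-hematological DLT leads to a hold. Section 6.2.1 continues: "If the toxicity resolves to meet eligibility parameters or baseline within 14 days of drug discontinuation, the patient may resume treatment at a reduced dose". Under 6.2.2, a DLT that "does not resolve to meet eligibility or baseline parameters within 14 days of drug discontinuation, the patient must be removed from protocol therapy".

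**Phosphate table, 6.4.**
- 7.0-9.0 mg/dL: withhold "erdafitinib treatment until serum phosphate level returns to" below 5.5 mg/dL or baseline, then restart at the same dose. A reduction is optional if the elevation persists beyond a week.
- Above 9.0 mg/dL: same recovery test, then restart at the reduced dose. The row has no upper bound.
- Above 10.0 mg/dL, and/or a renal change, and/or Grade 3 hypercalcemia: "Erdafitinib should be discontinued permanently". The drug may be re-introduced at the reduced dose if the child is benefiting and the study chair agrees.

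The table sets no removal deadline. Its footnote a suggests a 7-day interruption.

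**Precedence.** Sections 6.3 and 6.6 and the visual disturbance table refer back to 6.2, but 6.4 does not. Section 10.1(b) refers to Section 6 as a whole.

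**The concern.** A phosphate DLT belongs to two sets of rules at once. The sets differ on the recovery test, on whether there is a deadline, on the restart dose, and on when stopping is permanent. Without an order of precedence, two sites could act differently on children with the same laboratory course, and both could cite the protocol.

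The first stake is safety: whether a child goes back on drug, and at what dose. The second is the tolerability aim (1.2.2), because DLT and removal counts would partly reflect which section a site followed. The third is time on drug. These paths are likely to be used, since the protocol describes a rise in phosphate as an expected, exposure-related effect (2.2.1) and lists hyperphosphatemia among the likely adverse events (9.1.2).

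**Working it through.** No arithmetic applies. Each event below is assumed to be attributed to the drug, and is traced first through 5.4.1 and then through 6.2 and 6.4.

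| Event | DLT under 5.4.1? | Action under 6.2 | Action under 6.4 |
|---|---|---|---|
| A. Phosphate 9.5 mg/dL; first below 5.5 on day 20, baseline not reached by day 14 | Yes: 6.4 itself calls for a reduced dose, a dose modification on any reading | Removal (6.2.2) | Restart at reduced dose |
| B. Phosphate 10.5 mg/dL, back to baseline by day 10 | Yes | May resume at reduced dose (6.2.1) | Row above 9.0: restart at reduced dose. Row above 10.0: permanent stop unless the exception applies |
| C. Grade 3 hypercalcemia, resolved by day 10 | Yes: not among the exclusions | May resume at reduced dose (6.2.1) | Permanent stop unless the exception applies |
| D. Phosphate 8.0 mg/dL, recovered by day 7 | Only if a hold counts as a dose modification | If a DLT, resume at reduced dose; if not, 6.2 does not apply | Restart at same dose |

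**A** is the clearest conflict: one section restarts and the other removes. Neither 6.2.2 nor the row above 9.0 has a study chair exception that would bridge the two.

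**The recovery tests also differ.** Section 6.4 uses below 5.5 mg/dL or baseline. Section 6.2 uses eligibility parameters or baseline, and 4.1.7 has no phosphate criterion. Two readings of 6.2 follow:
- Only baseline is left as the test. Then A ends in removal under 6.2.2.
- With no limit set, any phosphate value meets eligibility. Then 6.2.2 never removes for phosphate, and 6.2.1 would permit resumption while 6.4 still requires a hold.

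The sections disagree on either reading.

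**B** conflicts inside 6.4 alone, because 10.5 exceeds both 9.0 and 10.0. **C** is a difference between a permission (6.2.1) and a default stop (6.4). **D** depends on a term the protocol does not define. The 7.0 threshold in 5.4.1.4 is where 6.4 first withholds drug, which supports counting a hold, but the text does not settle it.

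**Smallest children.** For BSA 0.53-0.74 m² the dose-reduction column of Appendix IV reads off protocol therapy. Case A then ends in removal under both sections. Case D becomes same dose under 6.4 against removal under 6.2.1, if a hold counts.

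**The case against.** The best defence is that the sections are cumulative. Section 5.2 lets a cycle start only if all of Section 6.0 is satisfied. Section 6.2.1 permits resumption but does not require it, so a site that follows the stricter last row of 6.4 does not breach 6.2.1. On the row overlap, a reader at 10.5 mg/dL finds a dedicated row for values above 10.0 just below. On deadlines, 6.4 is silent and 6.2.2 can be read as supplying one. The study chair is told of any DLT within 24 hours (5.3) and of any dosage modification (6.0), so sites do not work in isolation. The suggested 7-day interruption should make a hold beyond 14 days less common.

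Much of this stands for B and C. There the conflict matters only for a child without clinical benefit or without the chair's agreement, and the more specific row is a natural choice. A reader might infer that the two sections command flatly opposite actions for hypercalcemia. They do not: one permits, and the other stops by default with an exception.

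The defence does not settle A. The cumulative reading gives removal, the reading in which the specific section governs gives restart, and the protocol adopts neither. Section 6.4 calls itself general guidelines, while 6.2.2 is mandatory. Notifying the chair is not a rule of precedence, and footnote a suggests a duration without setting a limit. The exception in the last row also carries a footnote marker c with no matching text in the copy read. That may be a conversion loss, and nothing here rests on it.

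**Conclusion.** The inconsistency is real and in the current text. It is firmest for a phosphate DLT that recovers after day 14, is plain but milder for the row overlap and for Grade 3 hypercalcemia, and is conditional for 7.0-9.0 mg/dL. The comparisons with 6.2 assume attribution to the drug, and for phosphate that the event is a DLT under 5.4.1.4.

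Its frequency cannot be given. Three stronger conclusions are tempting, and the documents do not support them:
- A reader might scale the 9 of 99 adults with a dose reduction for hyperphosphatemia (2.2) to a 20-patient cohort. That figure counts adult dose reductions. It does not count holds in which the two recovery tests disagree, and no time-to-recovery data are given. The any-grade rates of 73.7% and 72.7% in two adult studies do not measure it either.
- A reader might infer that the primary decision is at risk. Under 11.5 an eligible child with at least one dose stays evaluable for response, so the 20-patient denominator and the 3-response rule are unchanged. Time on drug can differ, but its effect on response cannot be derived from the documents.
- A reader might infer that any child below 5.5 mg/dL but above baseline on day 14 must be removed. That needs a peak value that makes the event a DLT, and the baseline-only reading of 6.2.

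This is a safety-relevant drafting inconsistency that should be corrected. It is not a flaw in the sample size or the decision rule.

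**What to change.** Reconcile 5.4.1.4, 6.2 and 6.4:
- State which section governs phosphate elevation, hypercalcemia and renal changes, with a cross-reference in both 6.2 and 6.4.
- Say whether a hold alone is a dose modification for 5.4.1.4.
- Say how recovery is judged for phosphate under 6.2, given that 4.1.7 has no phosphate criterion.
- Remove the overlap between the rows above 9.0 and above 10.0 mg/dL.

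The thresholds, any deadline and the restart rule are for the study's clinicians to choose, and this point favours none of them. The cost is a wording amendment to three sections, with no new data and no change to the sample size or analysis.
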